#### *4.2.2. Chronic Splanchnic vein thrombosis*

Chronic Splanchnic vein thrombosis is defined by incident SVT with chronic thrombi on 2 serial imaging tests with an at least 3 months interval.

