## Study schedule

	Visit 0: Clinical assessment	Visit 1: Enrolment	Visit 2: MRDTI (within 48 hours of visit 1 in acute SVT)	Visit 3: 90-day follow-up
Check for inclusion/exclusion criteria		X		
Obtain informed consent		X		
Medical history		X		
Demographic data		X		
Clinical examination		X		
Laboratory test (D-dimer, renal function)		X*		
Doppler ultrasound, CT or MRI of the abdomen	X*			
Treatment decision	X			
MRDTI of abdomen			X	
Recording of				
Death				X
Major bleeding				X
Hospital admission				X
Symptomatic SVT or VTE				X

\*Part of clinical practice, no study proceedings

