## **5.2 Inclusion criteria**

1. Patients with confirmed acute SVT; definitions provided in paragraph 4.2 (Cases, group 1)
2. Patients with confirmed non-symptomatic chronic SVT defined by incident SVT with chronic thrombi on 2 serial imaging tests with at least 3 months interval (controls, group 2)
3. Aged 18 years and older
4. Willing and able to give informed consent

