## 7.2 Data analysis

### 7.2.1. Primary endpoint

A diagnosis (acute SVT, no signs of acute SVT, or non-diagnostic) for each arm of interest based on an aggregate reading of the MRDTI images will be made by two independent expert readers. A third reader will be involved to resolve any dispute. The sensitivity of MRDTI is determined by calculating the proportion of scans that are read as "positive for acute SVT" in patients with a confirmed acute SVT and the specificity is determined by calculating the proportion of scans that are read as "no signs of acute SVT" in patients with chronic SVT. The corresponding exact 95% confidence interval for each of the point estimates will be calculated. In addition to these estimates, sensitivity and specificity estimates with corresponding 95% confidence intervals will be calculated for the initial independent assessment of each of the two readers participating. A point estimate of the sensitivity of >90% will be acceptable for initiating a future management study.

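### Controls have no limit on the time from the later qualifying scan to MRDTI, so veins that reopen in between could raise specificity for chronic thrombus

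*Combined protocol and SAP*

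**What the plan says.** Section 4.2.2 defines chronic SVT as "incident SVT with chronic thrombi on 2 serial imaging tests with an at least 3 months interval". Inclusion criterion 2 in section 5.2 repeats this: "Patients with confirmed non-symptomatic chronic SVT defined by incident SVT with chronic thrombi on 2 serial imaging tests with at least 3 months interval". Both set a minimum gap between the two scans. Neither sets a maximum gap between the second scan and the study MRI.

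The Study schedule does not supply one. Its MRDTI column is headed "Visit 2: MRDTI (within 48 hours of visit 1 in acute SVT"), so the window excludes controls, and it runs from enrolment rather than from the qualifying scan. Conventional imaging ("Doppler ultrasound, CT or MRI of the abdomen") is listed only at Visit 0, carries no date limit, and is footnoted "Part of clinical practice, no study proceedings".

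Section 7.2.1 allows three readings: "A diagnosis (acute SVT, no signs of acute SVT, or non-diagnostic"). It then says that "the specificity is determined by calculating the proportion of scans that are read as" showing no acute SVT, among patients with chronic SVT. Section 4.3 states that the inversion time is chosen so that blood gives no signal. Section 1 names differentiation of acute from chronic SVT as part of the primary hypothesis.

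**The concern.** Specificity answers the acute-versus-chronic question only in controls who still carry a thrombus when MRDTI is done. If a vein reopens after the second qualifying scan, MRDTI should show no bright signal there, because blood is nulled. That reading falls in the same category as a persistent old thrombus correctly read as not acute. No reading category, exclusion or sensitivity analysis separates the two, and no conventional scan is planned alongside MRDTI. The planned data could therefore not show afterwards how many controls were uninformative.

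Specificity is half of the primary endpoint. The clinical need described in the Synopsis and section 2.3 is to judge the age of a thrombus that has been seen, and a patent vein does not test that.

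**Working it through.** **Inputs from the documents.** There are 35 controls, the expected sensitivity is above 90%, and the stated precision is about ±15% (section 7.1). Confidence intervals are exact 95% intervals (section 7.2.1). MRDTI specificity in leg DVT is 91%, 100% and 100% in the three studies of section 2.4.1. No expected specificity for SVT is stated.

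**Assumptions.** k of the 35 controls have no thrombus left at MRDTI, and all of these are read as negative. S is the specificity in controls with persistent thrombus. The documents do not give k; the values 4, 7 and 12 only show a range.

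**The plan's own figure.** The exact interval for 32/35 = 91.4% is 76.9% to 98.2%. The lower arm is 14.5 points and the upper arm 6.8. The stated ±15% is reproduced as the longer, lower arm.

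**Inflation.** With f = k/35:

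observed specificity = (1 − f) × S + f, so inflation = f × (1 − S).

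| k (f) | S = 100% | S = 91% | S = 80% (assumed) |
|---|---|---|---|
| 4 (11.4%) | 0 | 1.0 | 2.3 |
| 7 (20.0%) | 0 | 1.8 | 4.0 |
| 12 (34.3%) | 0 | 3.1 | 6.9 |

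Entries are percentage points. For example, 12/35 × 0.09 = 3.1 points and 12/35 × 0.20 = 6.9 points.

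**Same effect in counts.** Four false positives give 31/35 = 88.6% (exact interval 73.3% to 96.8%). If 7 of the 35 had recanalised, the figure for persistent thrombus is 24/28 = 85.7% (67.3% to 96.0%).

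**Precision.** With no false positives there is no bias, but the informative sample is still smaller. The exact lower limit is 90.0% for 35/35 and 87.7% for 28/28.

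**Opposite direction.** A control with new thrombus since the last scan, read as acute, counts as a false positive. Each such control takes 1/35 = 2.9 points off specificity. At S = 91%, one would nearly cancel the 3.1 points gained from 12 recanalised controls.

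**The case against.** A reader might infer that controls need not show persistent thrombus at all. The text does not support that: thrombus must be present on both scans at least 3 months apart, so a vein already open at the second scan is excluded. Only later recanalisation is at issue, and the documents do not say how often it occurs.

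The text also leans towards a current diagnosis. Controls must be confirmed cases of chronic SVT, section 4.4 has a final diagnosis made before inclusion, and Visit 0 imaging precedes enrolment. This makes very old scans an edge case. It does not rule them out, because none of these statements carries a date limit.

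The size may be small. Every MRDTI specificity in the documents lies between 91% and 100%. The closest comparison in section 2.4.1, recurrent leg DVT against residual clot, gave 100% (95% CI 92 to 100). In that range the inflation is at most about 3 points for up to 12 of 35 controls, well inside the planned precision. These are leg-vein data, so a lower value in splanchnic veins cannot be excluded, but 80% is an assumption with no source in the documents.

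Finally, a recanalised control truly has no acute SVT. Its scoring is correct for the Synopsis endpoint, which concerns diagnosis of acute SVT. The objection stands for that endpoint, but not for the acute-versus-chronic hypothesis in section 1 or for section 6.1, which names both acute and chronic SVT.

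**Conclusion.** The gap is real and its effect is conditional. As written, the plan can count controls without current thrombus towards specificity and has no means of identifying them afterwards. Inflation requires that some controls have recanalised, that these read negative, and that specificity in persistent thrombus is below 100%. For 4 to 12 of 35 controls it is 0 to 3.1 points over the 91–100% range cited for leg DVT, and 2.3 to 6.9 points at an assumed 80%. Precision for persistent thrombus is overstated even where the bias is zero.

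Two stronger conclusions are tempting. One is that specificity will be inflated. This is not established, because neither the recanalised share nor the frequency of new thrombus is given, and the two act in opposite directions. The other is that the decision on a future management study is compromised. It is not: section 7.2.1 bases that decision on the sensitivity point estimate alone and sets no specificity threshold.

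The change is still worth making, because the acute-versus-chronic claim rests on these controls.

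**What to change.** - **Sections 4.2.2 and 5.2 (criterion 2):** state a maximum interval, chosen by the sponsor, between the later qualifying scan and MRDTI. Require that scan to show thrombus still present in the named vein.
- **Study schedule:** give controls their own Visit 2 window, and record the dates of both qualifying scans at Visit 1.
- **Section 7.2.1:** report specificity in controls who meet the interval alongside specificity in all controls, including any already enrolled, with the number in each set and exact intervals.

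The cost is protocol wording, two date fields and one further estimate. The downside is a somewhat smaller pool of controls. Section 7.1 says chronic diagnoses exceed acute ones, but controls must also match cases on site and risk factor, with at least five patients per site, and rare sites such as BCS will feel the restriction most. The interval should therefore be long enough for routine follow-up scans to suffice, so that no study-only imaging is needed.

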### **4.3. MRDTI**

MRDTI will be performed as described before with a 1.5 or 3.0 Tesla unit using a T1-weighted magnetisation prepared three-dimensional gradient-echo sequence. The sequence includes a water-only excitation radiofrequency pulse to abolish the fat signal, and the effective inversion time is chosen to nullify the blood signal. Imaging will be performed of the affected veins in two imaging blocks with a total acquisition time of 8-12 minutes by using a 55-cm body coil.

### **4.4. Therapeutic management**

This is not a management study: before inclusion in the study, a final diagnosis and management plan, i.e. initiation of anticoagulant treatment or not, is made and discussed with the patients. The MRDTI findings are not used for this decision process. When venous thrombosis at any anatomical site is diagnosed during follow-up, treatment with therapeutically dosed anticoagulants will be initiated without delay, according to current guidelines.

## **5. Subjects**

### **5.1 Population base**

Consecutive patients with confirmed acute symptomatic SVT, who fulfil all the inclusion criteria and meet none of the exclusion criteria, are eligible for inclusion, as are patients with confirmed chronic

SVT. It is planned to enrol 73-75 subjects in the Rhea study (see paragraph 8.1 for detailed sample size considerations).

## **5.2 Inclusion criteria**

1. Patients with confirmed acute SVT; definitions provided in paragraph 4.2 (Cases, group 1)
2. Patients with confirmed non-symptomatic chronic SVT defined by incident SVT with chronic thrombi on 2 serial imaging tests with at least 3 months interval (controls, group 2)
3. Aged 18 years and older
4. Willing and able to give informed consent

## **5.3 Exclusion criteria**

1. MRI contra-indication (including but not limited to a cardiac pacemaker or subcutaneous defibrillator; vascular clips in the cerebral vessels; metal splinter in the eye, a hearing aid that cannot be removed; a neurostimulator that cannot be removed; a hydrocephalus pump)
2. A medical condition, associated illness or co-morbid circumstances that precludes completion of the study procedures (MRI and 90-day follow-up assessment), including but not limited to life-expectancy less than 3 months, inability to lie flat, morbid obesity preventing use of MR and claustrophobia.
3. Patients with decompensated liver disease with Child-Pugh class C cirrhosis (since MRDTI evaluation will be inadequate in these patients)
4. Patients with suspected tumour thrombus

## 6. Study endpoints

### 6.1. Primary endpoint

The primary endpoint of this study is the sensitivity and specificity of MRDTI for the diagnosis of acute and chronic SVT.

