Study population	
Inclusion criteria
 
 
– Patients with confirmed acute SVT; definitions provided in paragraph 4.2 (Cases, group 1)
 
– Patients with confirmed non-symptomatic chronic SVT, defined by incident SVT with chronic thrombi on 2 serial imaging tests with at least 3 months interval (controls, group 2)
 
– Aged 18 years and older
 
– Willing and able to give informed consent
 
 
Exclusion criteria
 
 
– MRI contra-indication (including but not limited to a cardiac pacemaker or subcutaneous defibrillator; vascular clips in the cerebral vessels; metal splinter in the eye, a hearing aid that cannot be removed; a neurostimulator that cannot be removed; a hydrocephalus pump)
 
– A medical condition, associated illness or co-morbid circumstances that precludes completion of the study procedures (MRI and 90-day follow-up assessment), including but not limited to life-expectancy less than 3 months, inability to lie flat, morbid obesity preventing use of MR and claustrophobia.
 
– Patients with decompensated liver disease with Child-Pugh class C cirrhosis (since MRDTI evaluation will be inadequate in these patients)
 
– Patients with suspected tumour thrombus
 

Number of subjects	
73-75 patients will be enrolled: 3-5 patients for the optimization of the scan sequence, 35 patients with confirmed acute SVT and finally 35 patients with confirmed, non-symptomatic chronic SVT. It is predetermined that at least five

	patients of each SVT site (PVT, SpVT and BCS) and at least five patients of each SVT risk factor (oncologic, post-surgical and inflammatoir/infectious) will be included.
Primary endpoints	The sensitivity and specificity of MRDTI for the diagnosis of acute SVT
Secondary endpoints	The secondary endpoints are 1) optimized MRDTI scan sequences for SVT; 2) the assessment of interobserver agreement between the reviewers.
Study duration and planning	The total duration of this study is expected to be 3 years.
Number of sites	4

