## 1. Introduction and hypothesis

Compared to lower extremity deep vein thrombosis (DVT) and pulmonary embolism (PE), very little research has focused on the diagnostic management of splanchnic vein thrombosis (SVT).[3] The tests that are currently used to diagnose SVT, doppler ultrasound (DUS) and computed tomography angiography (CTA), have a number of limitations, particularly related to patient safety. For example, CT angiography involves the use of ionizing radiations and iodinated contrast agent, with potential renal toxicity or allergic reactions. DUS has the advantage of being relatively inexpensive and widely available. It is however operator-dependent and the accuracy can be limited by body habitus and the presence of intestinal gas.[3] Importantly, whereas the diagnosis of symptomatic SVT is often challenging, the correct diagnosis of acute versus chronic SVT is even more difficult, as neither of the current available imaging tests is helpful in determination of the age of the thrombus or its clinical relevance. Due to this impossibility to determine whether the incidentally observed thrombosis is acute, chronic or even an imaging artefact, the vast majority of patients with incidental SVT are treated with -often lifelong- anticoagulants. It is widely acknowledged that this practice likely results in overdiagnosis and unjust exposure to anticoagulant therapy with associated risk of bleeding. In the proposed study we will evaluate whether magnetic resonance direct thrombus imaging (MRDTI) is a valid, reliable, safe and effective alternative for the diagnosis of acute and chronic SVT. Our primary hypothesis is that MRDTI will demonstrate acceptable sensitivity and specificity for the diagnosis of acute SVT and the differentiation between acute and chronic SVT.

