## **2.4 Magnetic Resonance Direct Thrombus Imaging as a Promising Alternative**

### *2.4.1. MRDTI for the lower extremity*

Magnetic Resonance Direct Thrombus Imaging (MRDTI) has been shown to be a highly accurate diagnostic method for a first deep vein thrombosis of the legs.[28, 29] The method is based on measurement of the T1 signal which shortens as a result of the formation of methemoglobin in a fresh thrombus.[30] This technique does not require the administration of gadolinium contrast and the acquisition time is short, making it a safe and patient-friendly test. MRDTI was found to have a high sensitivity of 95% and specificity of 91% for a first venography proven symptomatic DVT of the legs [31]. Moreover, interobserver agreement was excellent with a kappa-statistic of 0.89-0.98. A second study found even higher diagnostic accuracy with a sensitivity of 95% and a specificity of

100% [32]. Moreover, the positive signal disappeared in all patients after a period of six months.[32] In the subsequently performed Return-study, it was shown that MRDTI differentiated accurately between patients with confirmed recurrent ipsilateral DVT and those with asymptomatic residual intravascular clots and a normal D-dimer level with a sensitivity of 95% (95%CI 83-99) and a specificity of 100% (95%CI 92-100). This study additionally confirmed the high interobserver agreement with a kappa-value of 0.98.[28]

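### Does section 6.1, which adds chronic SVT to the primary endpoint, leave the primary analysis ill-defined?

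*Combined protocol and SAP*

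**What the plan says.** The primary endpoint is worded in two ways in current text. The synopsis has "The sensitivity and specificity of MRDTI for the diagnosis of acute SVT". Section 6.1 has "the sensitivity and specificity of MRDTI for the diagnosis of acute and chronic SVT". The primary objective (synopsis and section 3.1) also couples acute with chronic SVT.

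Section 7.2.1, whose text also stands in the synopsis, gives the calculation. Two readers assign each scan one of three results: "A diagnosis (acute SVT, no signs of acute SVT, or non-diagnostic". Sensitivity is the share of scans read as positive among patients with confirmed acute SVT. For the other measure, "the specificity is determined by calculating the proportion of scans that are read as" free of signs of acute SVT, among patients with chronic SVT. Exact 95% confidence intervals are planned for both. The go-ahead for a later management study depends on a sensitivity point estimate above 90%.

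Section 1 states its aim broadly, asking whether magnetic resonance direct thrombus imaging (MRDTI) "is a valid, reliable, safe and effective alternative for the diagnosis of acute and chronic SVT". The hypothesis that follows is narrower: acceptable accuracy "for the diagnosis of acute SVT and the differentiation between acute and chronic SVT". Section 5.2 admits as controls "Patients with confirmed non-symptomatic chronic SVT defined by incident SVT with chronic thrombi on 2 serial imaging tests", and the cases must have confirmed acute SVT.

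**The concern.** A primary endpoint should have one definition. Accuracy for acute and for chronic SVT could mean two separate accuracies, and the second is not available from these data. A chronic thrombus and an empty vein would both be read as showing nothing acute, so detection of chronic SVT cannot be measured. Everyone enrolled already has confirmed SVT, so specificity against absence of SVT cannot be measured either.

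The wider reading has some basis in the protocol. The section 1 aim speaks of diagnosing chronic SVT. The clinical problem described there includes telling true thrombus from imaging artefact. The Dutch title and the second objective in section 3.2 refer to suspected SVT. At stake is an unsupported conclusion: that MRDTI diagnoses chronic SVT, or that its specificity carries over to people without SVT.

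**Working it through.** **1. The plan's own precision figure.** Section 7.1 gives 35 patients per group, an expected sensitivity above 90% and a 95% interval of about ±15%. The exact interval is taken as Clopper-Pearson: lower limit = Beta quantile (0.025; x, n-x+1), upper limit = Beta quantile (0.975; x+1, n-x), with n = 35.

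| Correct reads | Estimate | Exact 95% CI | Distance to lower limit |
|---|---|---|---|
| 32/35 | 91.4% | 76.9-98.2% | 14.5 points |
| 33/35 | 94.3% | 80.8-99.3% | 13.4 points |
| 34/35 | 97.1% | 85.1-99.9% | 12.1 points |
| 35/35 | 100% | 90.0-100% | 10.0 points |

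The smallest count above 90% is 32, because 31/35 = 88.6%. Its lower arm of 14.5 points matches the stated figure; the upper arm is only 6.8 points. The stated precision therefore holds as an approximate bound, and it depends only on the group size and the count.

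**2. What can be estimated.** The cohorts contain 35 + 35 = 70 patients. Adding 3-5 pilot patients, who also have confirmed SVT, gives 73-75. Patients without SVT: 0. Readings that record a chronic thrombus: 0 of 3. Two quantities remain, and they are the two that section 7.2.1 names:

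- P(read acute | confirmed acute SVT), n = 35;
- P(read as nothing acute | confirmed chronic SVT), n = 35.

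**3. The wordings side by side.**

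| Place | Wording | Calculation it leads to |
|---|---|---|
| Synopsis endpoint | acute SVT | the two proportions in step 2 |
| Section 6.1 | acute and chronic SVT | the same, with acute and chronic read as the two groups |
| Section 1 hypothesis | acute SVT, and telling it from chronic | the same |
| Section 7.2.1 | explicit numerators and groups | the same |

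**4. Would a separate accuracy for chronic SVT add anything?** Suppose a negative reading is treated as a call of chronic SVT and every scan is diagnostic. Then sensitivity for chronic SVT equals specificity for acute SVT, and the reverse. The same two proportions are exchanged and nothing new is learned.

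Non-diagnostic scans break this identity. Take assumed counts of 31 positive, 2 negative and 2 non-diagnostic among 35 acute patients. Sensitivity for acute SVT is 31/35 = 88.6%. Specificity for chronic SVT is 31/35 = 88.6% if only positive reads count as correct, or (31 + 2)/35 = 94.3% if non-diagnostic reads also count as not chronic. That ambiguity belongs to a quantity that section 7.2.1 does not ask for.

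**5. The decision rule.** It uses one sensitivity, in acute SVT. Under either wording 32/35 passes and 31/35 fails.

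**The case for a change.** The best case for a change is that a primary endpoint should not depend on a charitable reading. The authors could state the contrast precisely, as their hypothesis shows, and rewording would cost no recruitment, imaging or analysis. A negative reading also cannot separate old thrombus from artefact, although the protocol presents artefact as part of the clinical problem.

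The textual mismatch stands, and so does the limit on interpretation. The rest does not carry the point further. No section claims specificity against absence of SVT. Section 4.1 labels the groups as cases and controls, section 4.4 requires a final diagnosis before inclusion, and section 4.3 images the affected veins. A reader can hardly miss that all participants have known SVT. The references to suspected SVT are in a title and an interobserver objective, and neither defines the endpoint.

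The background remark that in leg thrombosis "the positive signal disappeared in all patients after a period of six months" gives indirect support for expecting no signal in chronic thrombus. It concerns another site and a longer time than the 3-month minimum imaging interval for controls. The endpoint definition does not depend on it, because the planned specificity will measure this directly.

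Copying the synopsis phrase into section 6.1 would not settle the matter either. That phrase does not name the comparison group, and the primary objective would keep the broader wording.

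**Conclusion.** This is a clerical inconsistency that the plan resolves where it matters. Section 7.2.1 fixes both measures and the groups in which they are taken, and the hypothesis and eligibility criteria agree with it. The effect on every planned estimate, confidence interval, the sample size of 73-75 and the 90% rule is zero. Harmonising the phrases would be editorial tidying with no gain in the result.

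The conclusion rests on two assumptions. The first is that the analyst follows section 7.2.1, which carries the heading for the primary endpoint. The second is that the report presents the specificity as what it is: the share of patients with confirmed chronic SVT whose scan shows nothing acute. It should not be extended to patients without SVT. How non-diagnostic scans are counted is a separate question, and the wording of section 6.1 neither causes nor cures it.
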